9.4.3 Analysis of the Secondary Endpoint(s)

Our secondary endpoint aims to determine the feasibility and acceptability of the MBSR intervention and thus we will collect descriptive data to determine the feasibility and acceptability via program engagement. To assess program engagement: the # of MBSR group sessions attended will be calculated for each participant and the # and proportion of participants completing 50%, 75%, and 100% of group sessions will be calculated.

To assess preliminary efficacy, we will use the data as described for Primary Endpoint 2. Primary and secondary outcomes for the clinical trial are shown below.

| Outcome Type | Measures Used for Outcome | Definition of Outcome |
|--|---|--|
| Primary Efficacy Outcomes | TLFB, Urine Cotinine Test | The primary outcome measure is change in vaping frequency at the post-MBSR follow-up MRI session. |
| Primary Group Effect Outcome | FFMQ mindfulness scale, Difficulties in emotion regulation scale (DERS), General Substance Use History Questionnaire, Digit Span assessment | The primary outcome measure for the vaping vs TD group comparison will be the substance use, mental health and cognitive function measures at baseline. |
| Secondary Efficacy Outcomes | TLFB, FFMQ mindfulness scale, Difficulties in emotion regulation scale (DERS), Digit Span assessment | Secondary efficacy outcomes are changes in craving, mindfulness, negative emotions (depression, anxiety), emotion regulation and cognitive measures from baseline to post-MBSR study visit. |
| Primary Feasibility/Acceptability Outcomes | Recruitment, retention, program engagement, app use data | MT intervention will be considered acceptable and feasible for use in this population if at least 75% of participants are retained through the EOT, and at least 75% of participants download the C2Q app and complete 1 module. |
| Secondary Feasibility/Acceptability Outcomes | Participant self-report on MBSR program and CTQ utility, ease of use, etc. | Secondary outcomes for feasibility/acceptability are self-report responses about the helpfulness and utility of the MBSR program and C2Q app. |

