| | 
 - Engagement with MBSR training and post-training Craving-to-Quit app and change scores for other behavioral measure (e.g. vaping, emotion regulation). - rsFC from seeds such as dorsal anterior cingulate. |
| Study Population: | 40 nicotine vaping adolescents (13-18 years old) who vape 4-7 days per week, and 40 age, sex, race/ethnicity, SES matched typically developing (TD) adolescents with no nicotine vaping/tobacco smoking history. Participants will be recruited via online advertising, word of mouth, and from our vaping survey study. Recruitment will target the greater Baltimore area. To improve generalizability of our results, we will include youth who vape and who also smoke cigarettes (dual users) or co-use cannabis (co-MJ users) as well as those with stable psychiatric comorbidities. We will measure, control for, and exploratorily examine differences in these behaviors and groups in our analyses. |
| Phase or Stage: | This is a natural history study (comparison of teens who do and do not vape) and an open-label pilot study (comparison of teens who vape before and after MBSR training). |
| Description of Sites/Facilities Enrolling Participants: | The Biomedical Research Center of NIDA-IRP in Baltimore, MD, is the single site used for this study. |
| Description of Study Intervention: | The study intervention is a 9-week MBSR intervention once per week in-person or remotely (via an NIH approved remote platform used in compliance with policy, including HRPP Policy 303). The MBSR will be delivered to groups of 8-12 participants. Only the vaping adolescents will receive MBSR training. |
| Study Duration: | The study duration is approximately 24 months. |
| Participant Duration: | The participant duration is approximately 5.5-7 months, including baseline assessment and MRI scan 1, the 9-week MBSR intervention, and post-intervention assessment and MRI scan 2. There will also be a monthly follow-up for three months after the last MRI scan. Non-vaping participants will only complete baseline assessments and scan 1, which should take a week or less. |

Abbreviated Title: Mindfulness and Teen Vaping
Version Date: 07/21/2025
NIH IRB#: IRB001855

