1.3 Schedule of Activities

| Procedures | Pre-screening (Pre-consent) | Visit(s) 1 | Visits 2-10 | Visit 11 | Visits 12-15 |
|----------------------------------|--------------------------------|------------|-------------|----------|--------------|
| Eligibility Questionnaire Review | X | X | - | - | - |
| Informed Consent | - | X | - | - | - |
| Demographics | X | X | - | - | - |
| Clinical history | X | X | - | - | - |
| Nursing Eval | - | X | - | X | X |
| Outcome Evaluation | - | - | - | - | - |
| MRI scan | - | X | - | X | - |
| Questionnaires | - | X | - | X | X |
| MBSR training | - | - | X | - | - |
| Adverse Events Reporting | - | X | X | X | X |

Abbreviated Title: Mindfulness and Teen Vaping

Version Date: 07/21/2025

NIH IRB#: IRB001855

| TABLE 1. DIAGNOSTIC MEASURES AND ASSESSMENT BATTERY | | Visit #* | | | |
|--|--|-----------------|--------------|------------|---------------|
| DOMAIN | INSTRUMENT(S) | #1 | #2-10 | #11 | #12-15 |
| Diagnostic Assessment | Mini International Neuropsychiatric Interview for Children and Adolescents-DSM-5.0 version (MINI-KID-5) or SCID-RV | X | | | |
| Demographics and Puberty | Demographics questionnaire and Pubertal Development Scale | X | | | |
| MRI Safety | MRI Safety Assessment | X | | X | |
| Substance Use Measures | General Substance Use: Timeline Follow-back (TLFB) - 28 Days (V1), 7 Days (V12-15): tobacco vaping (vaping days and vapes or puffs/day), tobacco smoking, cannabis, alcohol, other drugs; Substance Use History Questionnaire; Cannabis Use Disorder Test (CUDIT); Craving Questionnaire | X | | | X |
| | E-Cigarette Measures (Vapers only): E-Cigarette Dependence Scale (EDS, 4 items); Modified Fagerstrom Test for Nicotine Dependence (FTND); Nicotine Social Influence Questionnaire (NSIQ) | X | | | X |
| | Biospecimens: Urine Cotinine Test, Urine Drug test (UDT), Breath CO and ALC tests | X | | X | X |
| Psychological Measures | Sensitivity to Reward and Sensitivity to Punishment Questionnaire (SRSPQ), Patient Health Questionnaire-9 (PHQ-9), General Anxiety Disorder-7 (GAD-7), Difficulty in Emotion Regulation Scale, 5-trial Adjusting Delay Discounting Task (bench), Momentary Impulsivity Scale | X | | | X |
| Mindfulness Measures | Five-Facet Mindfulness Questionnaire (FFMQ), Mindfulness Practice Questionnaire (MPQ) (Visits #3-15 only) | X | X (MPQ only) | | X |
| Cognitive Measures | Digit Span (DGS) assessment (forward and backwards) | X | | | X |

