Tobacco vaping has tripled among U.S. adolescents and few treatment options exist for young people who develop a vaping-related tobacco use disorder (TUD).⁴² In 2018, 4.1 million teens, *more than one out of every four U.S. high school students*, reported current tobacco product use, with 21% of those teens reporting use of nicotine via vaping (e-cigarettes).¹⁵ E-cigarette use is strongly associated with other tobacco product use (e.g. two-thirds of teen tobacco users are dual users who engage in both vaping and smoking).⁴³ In tobacco-naïve teens, vaping nicotine is associated with increased risk for progression to smoking.^{44,45} Further, use of e-cigarettes has not been shown to aid in smoked tobacco cessation in youth.⁴⁶ Compounding this issue, evidence-based treatment (EBT) options are limited for adolescents who vape nicotine and develop TUD.^{42,47} No clinical guidelines exist and few interventions have been developed for this population. *Development and testing of new treatments for youth TUD are desperately needed given the modest efficacy of current EBT for youth smoking⁴⁸ and lack of EBT targeting nicotine vaping in youth.*

Mindfulness Training: Neural Correlates, Psychological Mechanisms, & Role in Tobacco Cessation

Mindfulness is defined as “present-focused, non-judgmental awareness”.⁴⁹ Over the past two decades, numerous studies have shown that mindfulness can be increased with training and practice with resultant reductions in distress and improvements in emotion regulation.¹⁶ Furthermore, mindfulness training (MT) produces salutatory changes in brain structure, function, and connectivity.¹⁴ Given its ability to target distress tolerance and emotion regulation (two psychological phenotypes closely linked to treatment response for SUD/TUD), there is growing interest in adapting mindfulness-based interventions for use in TUD populations.⁵⁰

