8.1.2 Screening activities performed after a consent for screening has been signed

At the first visit, after consent/assent is obtained, the following measures will be gathered to further assess eligibility for the study:

Diagnostic Assessment (~1.5 hours)

- a. Clinical history – clinician review
- b. Mini International Neuropsychiatric Interview for Children and Adolescents-DSM-5.0 version (MINI-KID-5) or SCID-RV
- c. MRI Safety Assessment
- a. Substance Use History
 - General Substance Use History Questionnaire (with tobacco & e-cigarette smoking, alcohol, and cannabis questions included)
 - Cannabis Use Disorder Test (CUDIT, 8 items, ~1-2 min)

8.2 Study Evaluations & Procedures after eligibility has been determined.

Administration of questionnaires, interviews, or other instruments (Table 1).

Abbreviated Title: Mindfulness and Teen Vaping

Version Date: 07/21/2025

NIH IRB#: IRB001855

The consent, screening activities listed in 8.1.2, and the baseline assessments listed below may be completed in the same visit virtually or in-person, and all or some of these procedures may also be completed in the same visit as the first scan session. Some questionnaires may be completed virtually in between the consent appointment and Scan Day 1.

Orientation and Initial Baseline Assessments (Visit(s) 1, may be conducted virtually) (~35-55 min):

Demographics and Puberty (~2-5min)

- a. Demographics questionnaire
- b. Pubertal Development Scale

Substance Use Measures

- a. General Substance Use (all participants)
 - Timeline Follow-back (TLFB)
 - Past 28-days tobacco vaping (vaping days and vapes or puffs/day), tobacco smoking, cannabis, alcohol, other drugs if relevant. 7-day TLFB for later visits for vaping teens.
 - Craving Questionnaire (~1-5 min)
- b. E-Cigarette Measures (Vapers only)
 - E-cigarette Dependence Scale (EDS, 4 items, 1 min)
 - Nicotine Social Influence Questionnaire (NSIQ, 1 min)
 - Social influence - peer and family e-cigarette use and approval
 - Modified E-Cigarette Fagerstrom Test for Nicotine Dependence (FTND, 8 items, 1-2 min)

Psychological Measures

- Sensitivity to Reward and Sensitivity to Punishment Questionnaire (SRSPQ, 48 items, 5 min)
- Patient Health Questionnaire-9 (PHQ-9, 9 items, 2 min)
 - Assesses degree of depression severity
- General Anxiety Disorder-7 (GAD-7, 7 items, 2 min)
- Difficulty in Emotion Regulation Scale (36 items, 4 min)
- 5-trial Adjusting Delay Discounting Task (bench, 2 min)

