9.4.2 Analysis of the Primary Endpoints

Behavioral data analysis: Group differences (Vaping vs. TD) will be evaluated via chi-squares, independent t-tests (Primary Endpoint 1). In addition to EOT nicotine abstinence, Δ scores will be calculated for each behavioral measure (e.g. vaping frequency, emotion regulation) and will be used for within-subject analyses to characterize MBSR-related behavioral change (Primary Endpoint 2).

rsFC fMRI data analysis: Seed-based ROI whole-brain rsFC analyses between *a priori* defined hippocampal seed regions and large-scale brain networks (focusing on DMN, ECN, SN). Whole-brain regression analyses will be conducted for each seed on each individual's preprocessed data resulting in a Fisher-transformed z-value in each brain voxel (**DV**). Seed regions: Right- and left-whole and sub-region hippocampal ROI seeds such as those defined via probabilistic voxel maps created by Chase *et al.*⁹⁹ will be used for rsFC analyses. Target network identification: Hypothesis-driven seed-based analyses will be constrained to voxels within each of three functionally generated masks of large-scale brain networks (DMN, ECN, SN) identified via group independent component analysis⁶ or taken from a published atlas.

s-rsFC Analysis: Independent and Paired t tests will examine group (Vaping vs. TD) (Primary Endpoint 1) and session (Pre/Post-MBSR) (Primary Endpoint 2) effects in s-rsFC strength between each hippocampal seed and voxels within each of the 3 network masks (e.g., seed-ECN voxels).

d-rsFC Analysis: d-rsFC will be estimated using a sliding window method^{21,22} creating windowed correlation matrices, to which a k-means clustering algorithm will be applied to identify states.⁶ Independent and Paired t-tests will examine group (Vaping vs. TD) (Primary Endpoint 1) and session (Pre vs. Post-MBSR) (Primary Endpoint 2) differences in d-rsFC DVs: state occupancy and transitions.

Correlational analyses: To test relationships between MBSR-related Δ rsFC and Δ vaping behaviors and other behavioral outcomes, we will use regression analyses.

Post-hoc analyses: Post-hoc ROI seed-based whole-brain connectivity analyses will test if the regions showing mindfulness-related Δ rsFC are distinct from or overlap with regions modulated by nicotine exposure (from Primary Endpoint 1).

Abbreviated Title: Mindfulness and Teen Vaping

Version Date: 07/21/2025

NIH IRB#: IRB001855

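### The efficacy outcome counts vaping alone in a trial that enrols cigarette dual users, so replacing vaping with smoking would appear as improvement

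*Combined protocol and SAP*

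**What the plan says.** The outcome table in section 9.4.3 states: "The primary outcome measure is change in vaping frequency at the post-MBSR follow-up MRI session". The instruments in that row are "TLFB, Urine Cotinine Test". The table does not say how cotinine contributes to a vaping frequency. The secondary efficacy row covers craving, mindfulness, negative emotions, emotion regulation and cognition. No efficacy row covers cigarettes or total nicotine.

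The Synopsis says of the study population: "we will include youth who vape and who also smoke cigarettes (dual users) or co-use cannabis (co-MJ users". It sets no cap, and adds: "We will measure, control for, and exploratorily examine differences in these behaviors and groups in our analyses". Section 2.2 cites a background figure: "two-thirds of teen tobacco users are dual users who engage in both vaping and smoking".

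Smoking is recorded. The TLFB in Table 1 covers "tobacco vaping (vaping days and vapes or puffs/day), tobacco smoking, cannabis, alcohol, other drugs", and section 8.2 describes the baseline version in nearly the same terms.

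Three other provisions matter here:
- Section 9.4.2 opens its account of behavioural change with "In addition to EOT nicotine abstinence", then calculates change scores for each behavioural measure. It relates rsFC change to vaping change and to other behavioural outcomes by regression.
- Section 9.4.1 specifies paired t-tests for continuous measures.
- Section 9.4.5 uses semi-quantitative cotinine and breath CO to verify self-reported abstinence after MBSR.

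**The concern.** The outcome sees one product while the participants may use two. A dual user who stops vaping and smokes instead gets a large favourable change score although nicotine use continues. The two instruments in the same row would then point in opposite directions: vaping days fall, while cotinine, which reflects nicotine from any source, need not. No rule says which governs.

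Two uses of the score are at stake. First, section 2.2 says the pilot should supply preliminary efficacy data for later controlled trials and shed light on how MBSR may promote tobacco cessation in youth. A fall in vaping offset by smoking does not support that. Second, the regression in section 9.4.2 would treat a switcher as a strong behavioural responder although nicotine exposure continues. The same section then compares regions changed by mindfulness with regions modulated by nicotine exposure, so total exposure bears directly on interpretation.

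**Working it through.** The plan states no power, effect size or alpha for this outcome, so there is no figure to reproduce. The definitional point rests on reading; the arithmetic only shows scale.

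**What each measure registers.** Let V be vaping days and N be days with vaping or smoking, per 28. The Synopsis gives 4 to 7 vaping days per week, so V = 4 × 4 = 16 to 7 × 4 = 28 at baseline. (Section 5.1 admits teens from 10 days in 30, so some baselines may be lower.)

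| Teen | Change in V | Change in N | Nicotine abstinent? |
|---|---|---|---|
| Every vaping day becomes a smoking day | −16 to −28 | 0 | No |
| Smokes on the same days throughout, stops vaping | −16 to −28 | 0 | No |
| Stops vaping, never smokes | −16 to −28 | −16 to −28 | Yes |

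V cannot separate the first teen from the third. N separates them, but hides a real vaping reduction in the second. Neither measure is enough alone.

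**Effect on the group test, without noise.** Assume n = 40, k full switchers with a common baseline B, zero change in everyone else, and a two-sided 5% one-sample t-test on change.
- Mean change = −Bk/n.
- SD of change = B√[k(n−k)/(n(n−1))].
- Hence t = −√[k(n−1)/(n−k)], and B cancels.

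| k | Mean change in V (B = 16 to 28) | t | p |
|---|---|---|---|
| 3 | −1.2 to −2.1 | −√(3×39/37) = −1.78 | 0.083 |
| 4 | −1.6 to −2.8 | −√(4×39/36) = −2.08 | 0.044 |
| 8 | −3.2 to −5.6 | −√(8×39/32) = −3.12 | 0.003 |

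Mean change in N is 0 in every row, if switchers' smoking days exactly replace their vaping days.

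**With noise.** Adding normal variation to every participant's change (SD assumed 3 or 6 days, 4,000 simulated trials per cell), the share of trials with a significant fall in vaping is:

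| SD | B | k = 0 | k = 4 | k = 6 | k = 8 |
|---|---|---|---|---|---|
| 3 | 16 | 2% | 33% | 74% | 97% |
| 3 | 28 | 3% | 42% | 95% | 100% |
| 6 | 16 | 2% | 19% | 40% | 63% |
| 6 | 28 | 3% | 30% | 67% | 94% |

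This model is rough: symmetric noise lets a switcher finish below zero vaping days, which cannot happen. B comes from the Synopsis and n is the target for complete data. The values of k, the SD, the alpha level and zero change in the others are assumptions.

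**Do the existing provisions close the gap?**
- Cotinine is listed, but has no defined role in a frequency measure.
- Abstinence is binary. It denies a switcher the label of abstinent, but leaves the continuous vaping score unchanged.
- The promised control for dual use names no covariate or model, and a paired t-test has none. Adjusting for baseline dual use would not alter what the outcome counts.

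**The case against.** The best defence is that the outcome matches the hypothesis. Section 9.1 speaks of change in vaping behaviours and of preliminary efficacy to reduce vaping, and section 2.1 of reduction in tobacco vaping behaviours. Any-nicotine days answer a different question. This stands, and it is why the vaping outcome should be kept.

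The plan would also expose some switching. Smoking is on the TLFB, change scores are promised for each behavioural measure, the regressions extend to other behavioural outcomes, dual use is to be explored, and nicotine abstinence is analysed and biochemically verified. This stands in part: the information will exist, but nothing makes it bear on the efficacy conclusion.

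A reader might infer more than the documents support:
- That a switcher is classed as a treatment success. Efficacy has no responder rule or threshold; the 75% criteria concern feasibility and acceptability.
- That reduced nicotine exposure is a stated purpose. It is not.
- That two-thirds of this sample will be dual users. That figure describes teen tobacco users in general.
- That the protocol predicts switching. The progression it describes in section 2.2 is an association in tobacco-naïve teens, and nothing shows that MBSR participants move to cigarettes.
- That vaping frequency and nicotine abstinence are conflicting targets. They are complementary.

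**Conclusion.** The point holds as a gap in the outcome definition. The primary efficacy outcome is vaping frequency alone, dual users are enrolled, and no listed efficacy outcome covers smoking or total nicotine, so substitution would count as improvement and enter the rsFC regression as a large response. That conclusion needs no assumed numbers.

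Its size is unknown. The calculation shows only that if about one in ten participants switched fully and the others did not change, a nominally significant fall in vaping could arise with no fall in nicotine-use days. The documents give neither the switching rate nor the SD.

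The consequence is limited by rank. The formal primary endpoints in the Synopsis and section 3 are rsFC measures, and vaping change sits there under the secondary objectives of an open-label single-arm pilot. This is an inexpensive improvement to make before results are known. It is not a flaw that undermines the trial, and it does not justify replacing the vaping outcome.

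**What to change.** In the section 9.4.3 table and in section 9.4.2:
1. Keep change in vaping days as the efficacy outcome.
2. Beside it, prespecify change in days of any nicotine or tobacco use (vaping or smoking) from the same TLFB.
3. Put the planned nicotine abstinence outcome, verified by cotinine and CO, in the table, and state what role cotinine has otherwise.
4. State that a group fall in vaping days without a fall in any-nicotine days will be reported as possible product substitution and not as evidence of reduced tobacco use.
5. Repeat the rsFC regression with the any-nicotine change.

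While editing, reconcile the TLFB schedule. Table 1 shows none at Visit 11 and a 7-day version at Visits 12-15, whereas section 9.4.5 has a 28-day TLFB at the post-MBSR MRI visit. Both change scores need one visit and one window.

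The cost is wording, one derived variable and one further regression, with no new data. The efficacy conclusion may be less favourable. Any-nicotine days can also miss a real vaping reduction in a teen who smokes on the same days, which is why both should be reported.

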9.4.4 Safety Analyses

Abbreviated Title: Mindfulness and Teen Vaping

Version Date: 07/21/2025

NIH IRB#: IRB001855

N/A – This study does not involve any intervention presenting significant risk to participants.

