Technology-delivered Mindfulness Training has the potential to increase youth participation in TUD treatment. As a result of the pandemic, technology-delivered healthcare has expanded dramatically. The use of digital technology for smoking cessation holds promise for adolescents who do not typically access traditional treatments. Over 75% of young people own or have access to a smartphone⁷² and two-thirds report using a health-related mobile app.⁷³ Pbert et al.⁷⁴ recently published findings from a feasibility study showing that smartphone app-based MT with CravingtoQuit® was effective at reducing tobacco smoking in adolescents and reductions in smoking were correlated with app engagement. We propose to test engagement with this technology-delivered mindfulness-based cessation app after the group-based MT delivered via on-site or virtual sessions.

Need for Mechanism-focused Translational Research related to Mindfulness and Youth Vaping.

Although, substantial evidence has accumulated regarding the negative health effects and neural correlates of smoked tobacco products in youth and the beneficial effects of mindfulness and MBSR in adults, these phenomena are understudied in youth and in relation to vaped tobacco. This pilot study seeks to elucidate neurobehavioral correlates of daily tobacco vaping in adolescents, focused on static and dynamic rsFC, and to characterize the impact of participation in a MBSR intervention on rsFC and vaping behaviors. This pilot study is among the first to target vaping-related TUD in adolescents⁴² and will provide feasibility, acceptability, and preliminary efficacy data for MBSR which will inform next stage-controlled trials. As tobacco vaping youth represent a large, underdiagnosed, and vulnerable population⁷⁵, this protocol may elucidate the

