2.3 Risk/Benefit Assessment

2.4 Known Potential Risks

For both non-vaping control and vaping adolescent participants, there is minor risk associated with the MRI scans, including injury associated with bringing magnetic objects too close to the scanner, temporary hearing loss and very rarely minor burns. Trained personnel repeatedly screen participants and monitor use of earplugs to mitigate the risk of injury related to the strong magnetic field and noise from the scanner.

For vaping teens receiving the MBSR intervention, there is risk of breach of confidentiality associated with the group participation activities of the MBSR program.

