7.1 Discontinuation of Study Intervention/Experimental Manipulation

Participants who engage at any level in the MBSR training and are not disruptive will be allowed to continue with the intervention and the protocol in general. Only those who express a desire to withdraw from the MBSR, persist in disruptive behaviors during sessions, or are lost to follow-up will be discharged from the study. There are no safety endpoints that need follow-up after discontinuation of MBSR or the study.

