8.4.4 Time Period and Frequency for Event Assessment and Follow-Up

The occurrence of an adverse event (AE) or serious adverse event (SAE) may come to the attention of study personnel during study visits.

All AEs will be captured in the participant's NIDA IRP electronic research record, which is currently, the Clinical Data Warehouse (CDW). Information to be collected includes event description, time of onset, clinician's assessment of severity, relationship to study procedures (assessed only by those with the training and authority to make a diagnosis), and time of resolution/stabilization of the event. All AEs occurring while on study will be documented appropriately regardless of relationship. All AEs except those that are "Not Related" will be followed to adequate resolution/stabilization.

Any medical or psychiatric condition that is present at the time that the participant is screened will be considered as baseline and not reported as an AE. However, if the study participant's condition deteriorates at any time during the study, it will be recorded as an AE.

The events in the table below are very often seen with MRI and therefore fully expected (similar to minor bleeding or bruising after blood draws or injections). They will not be recorded as AEs because their occurrence does not constitute information that would inform or change the established risk profiles of MRI. Events solely related to conditions present at baseline, will also not be recorded as AEs.

Conditions Commonly Associated with MRI and Not to be Recorded as AEs:

| CTCAE Condition | CTCAE Grade | CTCAE Grade Description |
|----------------------------|-------------|--------------------------|
| General disorders: Fatigue | Grade 1 | Fatigue relieved by rest |

Abbreviated Title: Mindfulness and Teen Vaping

Version Date: 07/21/2025

NIH IRB#: IRB001855

| | | |
|--|---------|--|
| Ear and labyrinth disorders: Tinnitus | Grade 1 | Mild symptoms; intervention not indicated |
| Musculoskeletal and connective tissue disorders: Back pain | Grade 1 | Mild pain |
| Nervous system disorders: Dizziness | Grade 1 | Mild unsteadiness or sensation of movement |
| Nervous system disorders: Headache | Grade 1 | Mild pain |

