8.4.5 Adverse Event Reporting

In consultation with the PI, a trained member of the study team will be responsible for conducting an evaluation of all adverse events and shall report the results of such evaluation to the NIH Institutional Review Board (IRB) as per [Policy 801](#).

The PI will report all unanticipated adverse device effects (UADEs) to the Sponsor within 10 working days. This should be submitted to the ORSC RSS by a MedWatch Form (Form 3500A), which should be sent ENCRYPTED to the [contact] inbox with a cc to the CD/CMO/designee. The Sponsor will immediately conduct an evaluation to determine if the UADE presents unreasonable risk to subjects. If the Sponsor determines that the UADE presents unreasonable risk, part of the study presenting the risk or all of the study will be terminated within 5 working days of the determination, and no later than 15 working days after the Sponsor received notice of the UADE. For non-significant risk device investigations terminated due to an UADE, a sponsor may not resume a terminated investigation without IRB and FDA approval.

ALL AEs that are collected, as determined by the written protocol, should be tracked in the ORSC RSS's template AE tracker or similar document. All AEs will be sent to the Sponsor quarterly, or at minimum annually.

In addition, the PI will report to the Sponsor, within 5 working days, a withdrawal of approval by the reviewing IRB of the investigator's part of an investigation. The Sponsor will notify the FDA of withdrawal of IRB approval.

The PI will report to the Sponsor, within 5 working days, if the device is used without obtaining informed consent. The Sponsor will notify the FDA of use of the device without informed consent.

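### Section 9.4.4 plans no safety analysis, so the adverse events and mood scores the trial collects will not be summarised as harm

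*Combined protocol and SAP*

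**What the plan says.** Section 9.4.4 gives the safety analysis as N/A, with the reason that "This study does not involve any intervention presenting significant risk to participants".

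Other sections provide for collecting safety data:

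- The schedule in section 1.3 marks AE reporting at Visit 1, Visits 2-10, Visit 11 and Visits 12-15, which is every column after pre-consent screening.
- Section 8.4.4 states: "All AEs occurring while on study will be documented appropriately regardless of relationship". Severity, relationship and resolution are captured. Listed grade 1 MRI effects and events due solely to baseline conditions are exempt.
- Table 1 places PHQ-9 and GAD-7 at Visit 1 and Visits 12-15.
- Section 2.4 lists scan risks for all participants and says of the treated group that "there is risk of breach of confidentiality associated with the group participation activities of the MBSR program".

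On the use of the results, section 2.2 says the pilot will yield feasibility and acceptability findings and "preliminary efficacy data for MBSR which will inform next stage-controlled trials". Section 9.4.3 calls the intervention acceptable and feasible on two criteria, each at 75%: retention to end of treatment, and downloading the app and finishing one module.

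Section 7.1 ends its rule on stopping the intervention with "There are no safety endpoints that need follow-up after discontinuation of MBSR or the study".

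**The concern.** N/A here is a stated rule with a reason, so an analyst following the plan would produce no safety table. A low expected risk justifies a brief summary, but it does not explain why events that are collected and graded should go unsummarised.

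The treated participants are 13 to 18 years old, and some have stable psychiatric comorbidities. Planners of a later controlled trial would want an event rate, or a bound on one, and the number of teens whose depression or anxiety scores rose materially. The plan commits to neither. The acceptability rule contains no harm criterion, so it can be met whatever the events were.

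**Working it through.** No figure in the documents is in dispute. The check is textual, followed by a calculation of what a descriptive summary could deliver.

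**1. Is harm summarised anywhere else in section 9?**

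- Section 9.4.1 plans means, SDs and paired t-tests for changes in behavioural scores.
- Section 9.4.3 treats change in depression and anxiety as a secondary efficacy outcome. The measures listed for that outcome do not include PHQ-9 or GAD-7.
- Section 9.4.5 adds exploratory use of mood and anxiety measures.
- Section 9.4.8 promises a listing by measure and timepoint. AEs are not mentioned.

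None of these counts AEs, SAEs, harm-related withdrawals or teens who deteriorated.

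**2. Who is in the pre/post sets?** Section 9.3 requires completing the intervention (any number of sessions) and both scans, plus at least one follow-up visit for the behavioural outcomes. Section 7.1 discharges anyone who asks to leave MBSR. A teen who leaves in distress is therefore outside the mood analysis. Section 7.2 has the reason documented, but no analysis uses it. If retention is counted among those who start MBSR (an assumption, since the denominator is not stated), the 75% criterion still holds with 0.25 × 40 = 10 leavers of 40, or 0.25 × 60 = 15 of 60, whatever their reasons.

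**3. What would a table show?** Section 4.1 enrols up to 60 vaping teens to obtain 40 with complete data, so 40 and 60 bracket the number treated if the target is met.

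Upper 95% limit with no events: 1 − 0.05^(1/n) one-sided, 1 − 0.025^(1/n) two-sided.

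| n | One-sided | Two-sided |
|---|---|---|
| 40 | 7.2% | 8.8% |
| 60 | 4.9% | 6.0% |

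Exact (Clopper-Pearson) 95% intervals with n = 40: 1 event, 0.1% to 13.2%; 2 events, 0.6% to 16.9%; 4 events, 2.8% to 23.7%.

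Chance of at least one event, 1 − (1 − p)^n. The rates p are assumptions, as the documents give none:

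| p | n = 40 | n = 60 |
|---|---|---|
| 1% | 33% | 45% |
| 2% | 55% | 70% |
| 5% | 87% | 95% |
| 10% | 99% | 99.8% |

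**4. Can a mean conceal individual worsening?** Take an invented case: 6 of 40 worsen by 5 points and 34 improve by 2.

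- Mean change = (6 × 5 − 34 × 2)/40 = −38/40 = −0.95.
- Sum of squares = 6 × 5.95² + 34 × 1.05² = 249.9, so SD = √(249.9/39) = 2.53.
- t = −0.95/(2.53/√40) = −2.37, p = 0.023, in the direction of benefit.
- Yet 6/40 = 15% worsened (exact 95% CI 5.7% to 29.8%).

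This shows that it can happen, not that it is likely.

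**The case against.** The strongest reply is that safety is overseen and the gap is small. Much of that stands.

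- A reader might infer that harms go unmonitored. They do not. Section 8.4.5 says "All AEs will be sent to the Sponsor quarterly, or at minimum annually", sections 8.4.5 and 8.4.6 send evaluations to the IRB, and section 10.5 has the principal investigator review all data. What is missing is a planned summary.
- A reader might infer that mood is tested only for benefit. Section 9.4.1 states no direction and reports SDs, so an average worsening could appear. If the section 9.4.8 listing covers PHQ-9 and GAD-7, individual worsening could be read from it, though no count is planned.
- A reader might infer that early leavers disappear. Their reasons are documented, their on-study AEs are recorded, and their loss counts against retention. Poor attendance alone does not remove anyone from the pre/post sets.
- A reader might call the last sentence of section 7.1 a contradiction of section 8.4.4, which follows all AEs except unrelated ones to resolution. The first speaks of safety endpoints, of which the study has none, and the second of individual AEs. Both can be true. The wording is in tension because an AE still open at discontinuation could fall under either.

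Two further points limit any summary. Section 8.4.4 says only that events "may come to the attention of study personnel during study visits", and section 8.3 describes an explicit health query only at scan visits, so capture is partly passive and exact limits could suggest more certainty than exists. Also, counting any score above baseline would mislead: with no true change and symmetric noise, about half of the untied scores would be higher, and non-vaping controls have no follow-up to calibrate the count.

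These points shape the fix and keep the matter modest. They do not supply the missing summary.

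**Conclusion.** The point holds as a gap in planned analysis and reporting. Followed as written, the plan yields no event rate, no bound on one, no account of harm-related withdrawals and no count of teens who deteriorated. A summary could bound an unobserved event type at 7.2% (n = 40) or 4.9% (n = 60), one-sided, assuming complete capture and independent participants. Incomplete capture would make the true bound weaker. The single-arm design supports description only and cannot attribute events to MBSR.

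The documents do not support a claim that safety oversight is absent or that sections 7.1 and 8.4.4 flatly contradict each other. This is a cheap improvement and does not threaten the imaging objectives.

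**What to change.** Replace N/A in section 9.4.4 with a descriptive safety summary:

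1. **All vaping participants who attend at least one MBSR session, completers or not.** Give the number and percent with any AE, any related AE and any SAE, by grade, with exact 95% CIs. State which relationship categories of section 8.4.3.2 count as related. Add withdrawals with their documented reasons. State that AE capture is partly passive and that the single-arm design does not support causal attribution.
2. **Everyone scanned.** Tabulate recorded scan-related AEs, noting that the listed grade 1 MRI effects are not recorded by design. Report any known breach of confidentiality in the groups.
3. **Mood scores.** Beside mean change, give the number and percent whose PHQ-9 or GAD-7 worsens by at least a threshold that the study team fixes before analysis. Any increase at all should not count.

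The last sentence of section 7.1 and the AE follow-up statement in section 8.4.4 must be reconciled so that they read consistently. Which rule applies is for the study team to decide.

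The cost is one paragraph and a few descriptive tables with wide intervals. No visit or instrument is added.
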